The available information supports the conclusion that the risk/benefit ratio of the vaccines used in this trial is favorable. Therefore, the Sponsor increased the sample size of the study (see [Section 12.5](#)) and increased the attrition rate to ensure the adequate power to fulfil the endpoints (see [Section 9](#)).

Amendment 2

Due to the COVID-19 pandemic, the enrollment of subjects was put on hold on the 12th of March 2020 due to the increase number of cases in France. The ongoing vaccinations were stopped on the 16th of March 2020 due to the confinement established in the country and the consequent impossibility to follow study visits within requested time window. As the study vaccine is being administered in healthy individuals in a simulated schedule, there is no safety issue in case of incomplete vaccination.

Different measures were taken according to the stage of the vaccination:

- For subjects who have finished their vaccination scheme (3 subjects): the follow-up of the subject was monitored by phone. The 2 due visits V6 (D42), and V7 (D56) were replaced by phone call to monitor the safety (no blood sample was taken).
- For the subjects who have not finished their vaccination scheme (29 subjects): Subjects were withdrawn from the study due to protocol deviation (ie, inability to attend vaccination visit within allowed time windows), but they continue to be followed for safety (see [Section 5.2.11](#)). The follow-up of the subject will be monitored by phone.
- The 6-month follow-up will be done by phone as planned in the protocol.

These measures were taken by the Sponsor to ensure well-being of subjects (ie, to limit exposure to COVID-19) and were implemented without IRB/EC approval, as per national and international guidances. However, IRB/EC and health authorities were informed promptly about the measures reported in the current amendment.

The enrollment will resume as soon as subject's safety is ensured, and national health authorities approves. Therefore, in the current amendment, to replace withdrawn subjects, the Sponsor will increase the sample size of the study (see [Section 12.5](#)) to ensure the adequate power to fulfill the endpoints (see [Section 9](#)).

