- 1) For solicited reactions (except for fever) with an Investigator presence recorded as "No" in eCRF and with all daily records missing (unknown), and then all daily intensities will be derived as "None."
- 2) For a temperature partially missing after decimal point, the data will be analyzed replacing "MD" (missing data) by zero. For example, a "39.MD" daily temperature will be considered as "39.0°C" at the time of analysis.
- 3) For non-measurable solicited reactions, daily intensities will correspond to daily records reported in the clinical database. For measurable solicited reactions, the daily measurements reported in the clinical database will be converted based upon the intensity scales defined in the protocol; this assumes a reaction that is too large to measure (not measurable [NM]) is Grade 3. Note the intensity could be considered "None" (not a reaction) in the analysis despite being considered a reaction by the Investigator (eg, swelling measurement > 0 mm but < 25 mm).

Note: The maximum intensity on the ongoing period is derived from the record of the maximum intensity/measurement after the end of the solicited period following the rule described above.

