3.3.1.1.3 Presence

Presence is derived from the maximum intensity on the period considered:

- None: No presence
- Grade 1, Grade 2, or Grade 3: Presence
- Missing (Unknown): Missing presence

Subjects with at least one non-missing presence for a specific endpoint will be included in the analysis. Conversely, those without a non-missing presence will not be included in the analysis of the endpoint.

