- Solicited systemic reactions occurring between the first and the second injection, between the second and the third injection, and up to 7 days after the remaining injections.
- Unsolicited systemic AEs occurring between each injection and up to 28 days after the last injection.
- SAEs throughout the trial, ie, up to 6 months after the last injection.
- AESIs throughout the trial, ie, up to 6 months after the last injection.

In order to avoid any under-estimation of the incidences, the number of subjects with documented safety will be used as denominator of the frequencies.

- For solicited reactions, the denominator is the total number of subjects who have non-missing data for the particular category of reaction during the time period concerned.
Note: for solicited systemic reactions, if a reaction is ongoing at the time of the next vaccination, it will be treated differently depending on whether or not it has increased in intensity following the later vaccination.
 - If it has not increased in intensity after the next vaccination, it is to be attributed to the earlier vaccination, and is counted as just a single occurrence in safety analysis. The time of onset is the first day of the first occurrence in the earlier vaccination.
 - If it has increased in intensity after the next vaccination, it will be counted as 2 separate occurrences after each vaccination in safety analysis (the 2 occurrences will be attributed to the earlier vaccination and later vaccination, respectively). The date of the later vaccination will be considered as the end date for the first occurrence and the start date of the second occurrence, respectively.
- For unsolicited events, the denominator is the total number of subjects who were vaccinated at the dose analyzed (for the analyses after each dose) or the total number of subjects who were vaccinated at least one dose (for the analyses after any dose).

For safety parameters, 95% CIs of point estimates of proportion will be calculated using the exact binomial distribution (Clopper-Pearson method) for proportions [\(1\)](#).

30-minutes Post-Vaccination Observation Period

Unsolicited systemic AEs occurring within 30 minutes after each vaccination will be presented in summary safety tables, analyzed according to their causality (relationship to the study vaccine) and Grade 3 intensity.

Solicited Reactions

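### With all diary records missing, the SAP keeps an Investigator's No as a non-reactor but leaves a Yes out, which lowers reported rates of pain, headache, malaise and myalgia

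*SAP*

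**What the plan says.** SAP 3.3.1.1.1 (Daily Intensity) derives daily intensities in sequential steps. Step 1 covers every solicited reaction apart from fever. Where the Investigator has answered No, it reads "in eCRF and with all daily records missing (unknown), and then all daily intensities will be derived as" and ends with the value None. Step 3 covers everything else that bears on intensity: "For non-measurable solicited reactions, daily intensities will correspond to daily records reported in the clinical database", and measured reactions are converted with the protocol's scales. Step 3 also notes that a reaction reported by the Investigator can be analysed as None, for example a swelling under 25 mm.

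SAP 3.3.1.1.3: "Presence is derived from the maximum intensity on the period considered". It is not taken from the Investigator's field. If the maximum is Missing, presence is Missing, and "those without a non-missing presence will not be included in the analysis of the endpoint".

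SAP 4.1.2.2, on safety endpoints, gives the reason for the denominator: "In order to avoid any under-estimation of the incidences, the number of subjects with documented safety will be used as denominator of the frequencies". In the case of solicited reactions this means subjects with non-missing data for that reaction in the period concerned. SAP 4.3.2.4, on missing intensity of solicited reactions, only refers back to 3.3.1.1.1.

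In SAP 4.1.2.2 the maximum-intensity list for solicited reactions has Grades 1 to 3 only, while the list for unsolicited AEs also has a Missing category.

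**The concern.** The same eCRF field is believed when it says No and has no effect when it says Yes. A subject whom the Investigator judged free of a reaction is kept as a non-reactor. A subject whom the Investigator judged to have had one leaves both numerator and denominator. That sits badly with the stated wish to avoid under-estimating incidence. It also differs from SAP 4.3.2.2, which resolves a missing causality in the cautious direction, as related.

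Solicited reactions are a main part of the secondary safety objective, and protocol 9.2.1.1 makes the Investigator's assessment of them mandatory. An answer without diary grades is therefore a possible data pattern. If such cases were more frequent in one vaccine group, the descriptive comparison between groups would shift too.

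**Working it through.** **Inputs.** The rules come from SAP 3.3.1.1.1, 3.3.1.1.3 and 4.1.2.2. The documents give no rate or count for this data pattern, so there is no stated figure to reproduce. Missingness and reaction rates below are assumptions. N = 318 is the planned size of Group 1 (protocol 12.5).

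**Notation, per endpoint.** a = reactors by diary; b = non-reactors by diary; n = Investigator No, all days missing; y = Investigator Yes, all days missing.

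- SAP rate: a/(a+b+n)
- Both answers used: (a+y)/(a+b+n+y)
- Both answers ignored: a/(a+b)

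**Direction.**
- Both used minus SAP = y(b+n)/[(a+b+n)(a+b+n+y)]. This is never negative, and is positive when y > 0 and b+n > 0.
- Both ignored minus SAP = a·n/[(a+b)(a+b+n)]. This is also never negative.

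Enumerating 16,320 combinations of small counts gave no exception to either. If y = 0 and the Investigator's No is correct, there is no bias.

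**Size when missing records are unrelated to reacting and the Investigator is right.** Let p be the true incidence and m the share with an answer but no daily records. Then the SAP rate = p(1−m)/[(1−m)+m(1−p)] = p(1−m)/(1−mp).

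| p | m (assumed) | Calculation | Reported |
|---|---|---|---|
| 60% | 5% | 0.57/0.97 | 58.8% |
| 60% | 10% | 0.54/0.94 | 57.4% |
| 20% | 5% | 0.19/0.99 | 19.2% |

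**Size when half of the all-missing subjects are Yes (N = 318).** With 5% all-missing, 15.9 subjects have no records (7.95 Yes, 7.95 No) and 302.1 have diaries.
- Diary rate 30%: SAP 90.63/310.05 = 29.2%; both used 98.58/318 = 31.0%.
- Diary rate 10%: SAP 30.21/310.05 = 9.7%; both used 38.16/318 = 12.0%.

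Over diary rates of 5% to 50% and missingness of 1% to 5%, the shortfall with half Yes runs from about 0.25 to 2.4 points. If every all-missing subject is a Yes, the largest shortfall in that range is 4.75 points (diary rate 5%, missingness 5%).

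**Erythema and swelling.** Let q be the share of the y subjects whose reaction would truly reach 25 mm. With diary rate 10%, 5% all-missing and half Yes, the SAP rate is 9.74%. The true rate is (30.21 + 7.95q)/318:
- q = 0: 9.50%, so the SAP rate is 0.24 points too high.
- q = 0.5: 10.75%, so it is 1.01 points too low.
- q = 1: 12.00%, so it is 2.26 points too low.

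**Fever.** Step 1 does not apply, so Yes and No with all temperatures missing are treated alike, and both stay Missing.

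**The case against.** The strongest reply is that the case should be rare and that collection procedures are aimed at it. Protocol 11.1 has the Investigator interview subjects and clarify incomplete entries, 13.2 has the coordinator obtain missing diary data verbally and transfer it to the CRB, and 11.2 applies computerised checks for omissions. Protocol 12.3.1 expects very little missing safety data. This stands as a reason to expect a small effect. It does not supply a rule for the cases that remain.

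A second reply is that the sentence about under-estimation concerns the choice of denominator, that a recorded No is documented safety, and that SAP 3.3.1.1.7 openly lets measurements override an Investigator flag. This also stands in part: the tension with that aim is not a formal contradiction. But with no daily record at all, there is nothing to override the Investigator's Yes.

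Third, the shift is small beside sampling error. At 60% the approximate 95% half-width is 1.96·√(0.24/318) = 5.4 points in Group 1 and 1.96·√(0.24/106) = 9.3 points in a control group. The comparison is fair, but a systematic shift is not part of what the interval measures.

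A reader might infer more than the documents support:
- **That all solicited rates can only be biased downward.** Fever is excepted, and erythema and swelling can go either way.
- **That 5% missing is documented, because 29 + 3 = 32 of 636 subjects (5.0%) moved to phone contact in March 2020.** For the 29, protocol 5.4.1 says only "The follow-up of the subject will be monitored by phone"; it does not say that diaries were lost. Subjects complete diaries at home, and DC1 and DC2 are collected at V04 and V05, so at most the most recent diary is at risk.
- **That a Yes with some days None and the rest missing is counted as no reaction.** SAP 3.3.1.1.2 does not say how the maximum treats missing days.

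**Conclusion.** The asymmetry is real. The handling of No is stated; the loss of Yes is inferred from three SAP sections, but no other derivation is given. For pain, headache, malaise and myalgia with all daily records missing, the reported rate falls below the rate using both answers whenever such a Yes exists and at least one subject is counted as a non-reactor. For fever there is no such asymmetry, and for erythema and swelling the direction is uncertain.

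The illustrative loss is about 1 point (60% to 58.8%, 20% to 19.2%) at an assumed 5% with no daily records. It assumes that the Investigator is right and that missingness is unrelated to reacting. The actual number of subjects is not given and is probably small. The safety analysis is descriptive, so neither the non-inferiority tests nor the test against 95% is affected.

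**What to change.** 1. **Pain, headache, malaise, myalgia.** When Investigator presence is Yes and all daily records are missing, count presence as Yes with intensity Missing, and keep the subject in numerator and denominator. Add a Missing row to the solicited maximum-intensity table, as already exists for unsolicited AEs.
2. **Fever.** Do not extend the rule. Counting a fever Yes while a fever No stays missing would create an upward asymmetry.
3. **Erythema and swelling with no measurements.** Report the counts by vaccine group, and show a sensitivity table with these subjects counted once as present and once as absent.
4. **Labelling.** SAP 1.1 postdates the first database lock and unblinding, so present the result as a sensitivity analysis beside the planned table, not as a replacement.

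The cost is one added rule, one table row and a short supplementary table. Step 1 already relies on the Investigator's field, so no new data are needed. The downside for the sponsor is that reported rates become slightly less favourable.

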3.3.1.1.2 Maximum Overall Intensity

Maximum overall intensity is derived from the daily intensities computed as described in [Section 3.3.1.1.1](#) and is calculated as the maximum of the daily intensities over the period considered.

3.3.1.1.3 Presence

Presence is derived from the maximum intensity on the period considered:

- None: No presence
- Grade 1, Grade 2, or Grade 3: Presence
- Missing (Unknown): Missing presence

Subjects with at least one non-missing presence for a specific endpoint will be included in the analysis. Conversely, those without a non-missing presence will not be included in the analysis of the endpoint.

3.3.1.1.4 Time of Onset

Time of onset is derived from the daily intensities computed as described in [Section 3.3.1.1.1](#). It corresponds to the first day with intensity of Grade 1, Grade 2, or Grade 3.

Note: If a reaction is not continuous (ie, reaction occurs over two separate periods of time intervened by at least one daily intensity Missing or None) then the time of onset is the first day of the first occurrence.

Note: for solicited systemic reactions, if a reaction is ongoing at the time of the next vaccination, it will be treated differently depending on whether or not it has increased in intensity following the later vaccination.

- If it has not increased in intensity after the next vaccination, it is to be attributed to the earlier vaccination, and is counted as just a single occurrence in safety analysis. The time of onset is the first day of the first occurrence in the earlier vaccination.
- If it has increased in intensity after the next vaccination, it will be counted as 2 separate occurrences after each vaccination in safety analysis (the 2 occurrences will be attributed to the earlier vaccination and later vaccination, respectively). The date of the later vaccination will be considered to be the end date for the first occurrence and the start date of the second occurrence, respectively.

3.3.1.1.5 Number of Days of Occurrence During the Solicited Period

Number of days of occurrence over the solicited period considered is derived from the daily intensities computed as described in [Section 3.3.1.1.1](#). It corresponds to the number of days with daily intensities of Grade 1, Grade 2, or Grade 3. Number of days of occurrence on the solicited period with a specified intensity may also be derived.

3.3.1.1.6 Overall Number of Days of Occurrence

If a reaction is ongoing at the end of the solicited period, then the overall number of days of presence is derived from the daily intensities and the stop date of the reaction after the end of the solicited period. The overall number of days of presence is:

- (stop date – last vaccination date) + (number of days of presence within the solicited period) – length of the solicited period + 1

If the stop date is missing or incomplete (contains missing data [MD]), the overall number of days of occurrence will be considered as “Missing”.

3.3.1.1.7 Ongoing

Ongoing is derived from the last daily intensity of the solicited period computed as described in [Section 3.3.1.1.1](#) and the maximum intensity on the ongoing period. The investigator’s ongoing flag is not used because the measurement would determine the ongoing status of the reaction.

- Ongoing: if the last daily intensity of the solicited period is at least Grade 1 and the maximum intensity in the ongoing period is at least Grade 1
- Not ongoing: if the last daily intensity of the solicited period is None or the maximum intensity on the ongoing period is None.
- Missing: all other conditions (in this case, it is not included in the denominator of the ongoing analysis in the safety tables).

3.3.1.2 Unsolicited AEs (Including SAE and AESI)

3.3.1.2.1 Presence

An observation will be considered an event if it has at least a verbatim term and is not a Grade 0 intensity event.

Grade 0 events should not be included in safety analysis but are included in the separate listing “Unsolicited adverse events not included in the safety analysis.”

3.3.1.2.2 Intensity

Intensity for unsolicited AEs will be derived according to the following classification: None, Grade 1, Grade 2, Grade 3, or Missing.

If the unsolicited AE is measurable and its PT is part of the list of solicited reactions, then the measurement is derived based upon and following the same rule as the intensity scales defined in the protocol for that measurable injection site or systemic reaction. Note the intensity could be considered as “None” (not a reaction) in the analysis despite being considered a reaction by the Investigator (eg, swelling measurement > 0 mm but < 25 mm).

Intensity for the other unsolicited AEs will correspond to the value reported in the eCRF.

The maximum intensity corresponds to the highest intensity for a unique term.

3.3.1.2.3 Last Vaccination

Last vaccination before an unsolicited injection site AE is derived from the vaccination number in the “Vaccination” field provided in the eCRF.

Last vaccination before an unsolicited systemic AE is derived from the start date of the systemic unsolicited AE provided in the eCRF and is calculated as follows:

- If an unsolicited systemic AE has a complete start date and different to any of the vaccination dates, the start date is used to determine the last vaccination before the unsolicited AE
- If the start date is missing or partially missing, or equal to any vaccination date, then the visit number in the “Appeared after Visit” field, is used to determine the last vaccination before the unsolicited systemic AE

3.3.1.2.4 Time of onset

Time of onset is derived from the start date of the unsolicited AE and the date of last vaccination as described in [Section 3.3.1.2.3](#):

- Time of onset = start date of the unsolicited AE – date of last vaccination before the unsolicited AE

The time of onset should be considered as missing only if one or both dates are missing or partially missing.

An unsolicited AE with missing time of onset will be considered to have occurred just after the last vaccination (computed according to [Section 3.3.1.2.3](#)), so will be included in safety analysis. Note: Unsolicited AE that occurred before the first vaccination (negative time of onset) will not be included in safety analysis but will be listed separately.

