- 6) Inject the appropriate study vaccine (VAC5) in the opposite arm to that of VAC4 and at least 3 cm apart from the previous injection site.
- 7) Keep the subject under observation for 30 minutes, and record any AR in the source document.
- 8) Give the subject the third diary card (DC3).
- 9) Remind the subject to notify the site in case of a SAE and AESI.
- 10) For woman of childbearing potential: remind the subject to notify the site in case of pregnancy.
- 11) Complete the relevant source document information and CRF pages for this visit.

V06 (14 [± 3] days after VAC5): Collection of Safety Information and Blood Sample

- 1) Review the DC3 with the subject, including any AEs, SAEs, AESIs, medications, or therapy that occurred since vaccination by Investigator or delegate. The subject will continue using the DC3 to collect safety information until the next visit.
- 2) Conduct a physical examination.
- 3) Obtain the fourth 6 mL blood sample (see [Section 7.1](#) for detailed instructions regarding the handling of blood samples).
- 4) Remind the subject to notify the site in case of an SAE and AESI.
- 5) For woman of childbearing potential: remind the subject to notify the site in case of pregnancy.
- 6) Complete the relevant source document information and CRFs for this visit.

V07 (28 [± 3] days after VAC5): Collection of Safety Information

- 1) Review and collect the DC3 with the subject, including any AEs, SAEs, AESIs, medications, or therapy that occurred since vaccination by Investigator or delegate.
- 2) Conduct a physical examination.
- 3) Give the subject with the MA to record any SAEs or AESIs that may occur during the 6-month safety follow-up.
- 4) Remind the subject to notify the site in case of a SAE, and AESI.
- 5) For woman of childbearing potential: remind the subject to notify the site in case of pregnancy.
- 6) Complete the relevant source document information and CRF pages for this visit.
- 7) Complete the trial termination record.

Contact Telephone Call (6 months [$+14$] days] after VAC5; ie, D180 to D194 after VAC5): Collection of Safety Information

- 1) Review MA by a qualified person Investigator or delegate, including any AEs, SAE, AESIs, medications or therapy, and pregnancy for woman of childbearing potential that occurred since last visit.
- 2) Complete the relevant source document information and appropriate CRF.

Follow-up of subjects with Related AEs or with AEs That Led to Study/Vaccination Discontinuation:

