- *Intensity grade: the maximum intensity grade will be computed during the solicited period for all solicited reactions and overall for ongoing solicited reactions.*

Unsolicited Adverse Events

The unsolicited systemic AEs will be analyzed:

- “Between the first and the second vaccine injection”, which corresponds to AEs reported at V02 and occurring after the first vaccine injection^a

^a For subjects interrupting their vaccination schedule after the first injection, unsolicited AEs until 28 days after the first injection will be collected

- “Between the second and the third vaccine injection”, which corresponds to AEs reported at V03 and occurring after the second vaccine injection ^a
- “Between the third and the fourth vaccine injection”, which corresponds to AEs reported at V04 and occurring after the third vaccine injection ^b
- “Between the fourth and the fifth vaccine injection”, which corresponds to AEs reported at V05 and occurring after the fourth vaccine injection ^c
- “Within 28 days after the fifth vaccine injection”, which corresponds to AEs reported at V07 and occurring after the fifth vaccine injection
- “Within 28 days after any vaccine injection”, which corresponds to AEs belonging to any of the five above categories

The unsolicited injection site reactions will be analyzed within 28 days (from D0 to D28) after each vaccination, and within 28 days after any vaccination. An unsolicited injection site reaction (**excluding SAE and AESI**) reported with an onset > 28 days after a vaccination will not be included in the safety analysis, but will be listed separately.

The unsolicited systemic AEs will be analyzed between each vaccination if vaccinations are separated less than 28 days, or up to 28 days after each vaccination, if vaccinations are separated by 28 days or more or the next vaccination is interrupted, and up to 28 days after any vaccination. An unsolicited systemic AE (**excluding SAE and AESI**) reported with an onset > 28 days after vaccination will not be included in the safety analysis, but will be listed separately.

Note: An unsolicited AE with missing time of onset will be considered to have **occurred within or up to 28 days after the last vaccination** (computed according to [Section 3.3.1.2.3](#)), so will be included in safety analysis.

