The unsolicited AEs will be summarized in the safety overview and analyzed according to their nature (SOC and PT of the MedDRA classification), causality (relationship to the study vaccine), time of onset, duration and maximum intensity.

The occurrence of any unsolicited AE will be presented after any and each injection according to:

- *Maximum intensity:*

- Missing
- Grade 1
- Grade 2
- Grade 3

^a For subjects interrupting their vaccination schedule after the second injection, unsolicited AEs until 28 days after the second injection will be collected

^b For subjects interrupting their vaccination schedule after the third injection, unsolicited AEs until 28 days after the third injection will be collected

^c For subjects interrupting their vaccination schedule after the fourth injection, unsolicited AEs until 28 days after the fourth injection will be collected

- *Time of onset categories:*

- Missing
- D0-D3
- D4-D7
- D8-D14
- $\geq D15$

- *Maximum duration:*

- Missing
- 1 - 3 days
- 4 - 7 days
- 8 - 14 days
- 15 days or more

SAEs and AESIs

In addition, the SAEs and AESIs, which are included in the unsolicited AEs, occurred during the study will also be analyzed on the following periods:

1. during vaccination period: from date of first vaccination (D0) to 28 days after the date of last exposure to study vaccine (date of last exposure + 28 days)
2. during the six-month safety follow-up period: from 29 days after the date of last exposure to study vaccine (date of last exposure + 29 days) to end of study (last visit date or contact date collected in eCRF)
3. during the study: from date of first vaccination (D0) to end of study [last visit date or contact date collected in eCRF])

SAEs will be analyzed according to their causality (relationship to the study vaccine), seriousness criteria, outcome and nature (SOC and PT of the MedDRA classification).

AESIs will be summarized and analyzed according to their nature (SOC and PT of the MedDRA classification) and causality.

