4.3.2.5 Start Date and Stop Date

Missing or partially missing start dates for unsolicited AEs will remain missing and not be imputed.

If either the start is missing or partially missing, the time of onset will be considered as missing.

Nevertheless, unsolicited AEs with missing time of onset will be included in analyses according to the visit collected.

Missing or partially missing stop dates for AEs (solicited reactions and unsolicited AEs) will remain missing and not be imputed.

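### The SAP's missing-onset rule ignores a known month and year, so a follow-up SAE or AESI can be placed within 28 days of vaccination, while other SAP text points the other way

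*SAP*

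**What the plan says.** SAP 3.3.1.2.4 defines when onset counts as missing: "The time of onset should be considered as missing only if one or both dates are missing or partially missing". A start date with a known month and year but no day therefore qualifies. The same section continues: "An unsolicited AE with missing time of onset will be considered to have occurred just after the last vaccination", and keeps the event in the safety analysis. The note under Unsolicited Adverse Events in SAP 4.1.2.2 repeats the rule with a window, treating such an event as having "occurred within or up to 28 days after the last vaccination". The dose concerned comes from SAP 3.3.1.2.3: when the start date is incomplete, the Appeared after Visit "field, is used to determine the last vaccination before the unsolicited systemic AE".

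SAP 3.3.1 and the SAEs and AESIs part of 4.1.2.2 both count SAEs and AESIs among the unsolicited AEs. The latter reports them over three periods: first vaccination to day 28 after the last dose; "during the six-month safety follow-up period: from 29 days after the date of last exposure to study vaccine" to the end of study; and the whole study. It gives no rule for partial dates.

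Two other statements bear on the point. SAP 4.3.2.5 leaves partial start dates unimputed and then says that "unsolicited AEs with missing time of onset will be included in analyses according to the visit collected". SAP 4.1.2.2 also defines the systemic AE category after the fifth dose by reference to events reported at V07.

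Under Protocol 5.1.4, follow-up ends with a telephone call 180 to 194 days after VAC5. Its first step is "Review MA by a qualified person Investigator or delegate, including any AEs, SAE, AESIs, medications or therapy".

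**The concern.** A default towards the vaccination window is sensible when nothing is known about timing. Here it also applies when the recorded month and year rule that window out, so usable information is discarded. The events exposed to this are SAEs and AESIs that start after V07 and have an incomplete date.

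SAE and AESI occurrence to six months is a secondary safety endpoint, and the SAP tabulates it separately for the vaccination and follow-up periods. If the rule is applied as written, a late event appears as an early one. If a programmer follows SAP 4.3.2.5 instead, it does not. The period tables should not depend on which paragraph the programmer happens to follow.

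**Working it through.** The plan states no figure to reproduce. The check is a reading of the derivation chain, with a calendar illustration.

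**Chain for one event.** Assumed dates: VAC5 on 15 January 2020; an SAE first reported at the six-month call with start date May 2020, day unknown.

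1. The start date is partial, so time of onset is missing (SAP 3.3.1.2.4 and 4.3.2.5).
2. The last vaccination is taken from the Appeared after Visit field (SAP 3.3.1.2.3). For a systemic event arising after V07 in a subject with all five doses, that is VAC5.
3. Onset is taken as just after VAC5 (SAP 3.3.1.2.4), or within 28 days of it (note in SAP 4.1.2.2).
4. The true onset lies between 1 May 2020 (day 107 after VAC5) and 31 May 2020 (day 137). Both bounds are later than day 28.
5. With a complete date, the same SAE would fall in the follow-up period.

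The bolded exclusion of SAEs and AESIs elsewhere in SAP 4.1.2.2 does not change this. It concerns events reported with an onset beyond 28 days, not events with missing onset.

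**The competing text.** SAP 4.3.2.5 speaks of inclusion by visit but does not say which period a visit or the telephone contact maps to. The post-dose-5 category refers to events reported at V07, which an event first reported at the call would not meet. Neither is written as an exception to the missing-onset rule, and neither note says it yields to them.

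**How often month and year would settle the matter.** Follow-up runs from day 29 to day 180 or 194 after VAC5, that is 180 − 28 = 152 or 194 − 28 = 166 possible onset days. For each of 365 consecutive assumed VAC5 dates starting on 1 October 2019, and each follow-up onset day, the earliest possible onset was set to the first day of the onset month. The day was counted as settled if (first of month − VAC5 date) > 28.

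| Follow-up ends | Onset days | Settled, average | Range by VAC5 date |
|---|---|---|---|
| Day 180 | 152 | 90% | 80–100% |
| Day 194 | 166 | 91% | 82–100% |

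The remaining days fall in months that overlap the 28-day window and stay ambiguous. These percentages describe possible onset days, not observed events.

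**What one event does to a table.** In a group of 106, moving from 0 to 1 event takes the rate from 0% (exact upper 95% limit 3.4%) to 1/106 = 0.94% (upper limit 5.1%). In Group 1 it goes from 0% (1.15%) to 1/318 = 0.31% (1.74%). Any single event has this effect. The figures show only the scale of one misplacement.

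**The case against.** The best reply is that the SAP does not firmly produce the misplacement. SAP 4.3.2.5 is the dedicated missing-data section, and its visit-based wording can be read as sending a call-reported event to follow-up. The V07 definition supports that reading. The SAE and AESI period block is also defined by date and does not itself invoke the missing-onset note. This stands as far as it goes: the literal result is one of two available readings. It does not dispose of the point, because the notes in SAP 3.3.1.2.4 and 4.1.2.2 are explicit and make no exception for SAEs or AESIs.

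A second reply is the two-step analysis. The first lock uses data up to D56, so call-reported events cannot enter tables produced then. That is correct for those tables. The SAP does not say how the vaccination-period SAE and AESI table is handled at the final lock. If it is not rerun, an event assigned to that period at that stage would appear in neither period's table, only in the whole-study one.

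Third, few dates are likely to be incomplete. Start and stop dates must be recorded (Protocol 9.2.1.3.3), SAEs are reported within 24 hours (10.1), the safety and clinical databases are reconciled (11.2), queries are completed before lock (13.4.1), and subjects hold a memory aid. This stands.

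Fourth, placing undated events near vaccination is conservative. That holds where the date is compatible with the window, and the fix keeps it there.

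**Conclusion.** The rule should be corrected, but its reach is narrow. As written, it can assign a follow-up SAE or AESI to the 28-day window against its own recorded month and year, and it conflicts with other SAP text on the same events. The effect is confined to how SAEs and AESIs are split between periods. The documents give no count of incomplete dates, so the number affected is unknown and probably small.

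Several stronger readings are tempting and not supported:

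- A reader might infer that every follow-up event with an incomplete date is certainly misplaced. The competing wording leaves that unsettled.
- A reader might infer a percentage inflation of the 28-day SAE count. That needs an assumed share of incomplete dates and a constant event rate; the documents supply neither.
- A reader might infer that SAEs are lost or that causality is altered. The whole-study table still counts each event. The investigator judges relatedness event by event, including the delay from vaccination (Protocol 9.2.1.3.5), the sponsor's safety officer also assesses SAEs (10.4), and the SAP summarises causality as collected, apart from its rule for missing relatedness.
- A reader might extend the point to non-serious AEs. Although the call checklist mentions AEs generally, collection after V07 is aimed at SAEs and AESIs, so these are barely affected.

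The 90% figure rests on assumed vaccination dates and treats every follow-up day alike.

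**What to change.** In SAP 3.3.1.2.4 and the note in 4.1.2.2, state that for a partial start date the known month and year are used first:

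- If the earliest possible onset is later than the last vaccination + 28 days, an SAE or AESI goes to the six-month follow-up period and any other AE is listed separately.
- If the latest possible onset is on or before that day, or the partial date is compatible with both periods, the event stays in the 28-day window as the conservative default.
- Only when the date is wholly missing does the visit or contact at which the event was collected decide the period.

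Add the same rule to the SAE and AESI periods in 4.1.2.2 and align 4.3.2.5 with it.

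The visit should not override date information. V07 is scheduled 28 ± 3 days after VAC5, so it can fall on day 25, and an event starting after it may still lie inside the vaccination period. Subjects withdrawn before completing vaccination and followed by phone (Protocol 5.4.1, Amendment 2) may have no V07 at all.

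The cost is SAP wording and a few lines of derivation code, with no new data. The downside is a slightly less conservative allocation, and only where the recorded date shows late onset or, for a wholly missing date, where the event was collected after V07. The SAP's version history already records an amendment after the first lock and unblinding, so any further change should be dated and applied identically in all groups.
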